The research activities involve a two-arm prospective RCT enrolling a sample of 600 AMSM with the aim of maintaining a randomized sample of approximately 500 online-recruited AMSM (13-18), assuming 15-20% attrition. After consent and completion of the online baseline survey, AMSM are randomized to either the control or experimental condition (Intervention, n=300; Control, n=300). Participants in the control arm will receive access to only the resource locator function of iReach, allowing them to search for local resources. Participants recruited nationally will receive a list of national resources. Participants in the experimental arm will receive access to all iReach functions, including life skills education, goal setting, local/national resource directory, a discussion forum related to life skills and goal setting, and the ability to link to a Peer Mentor through the VSee video-chat function. After consent and a baseline survey, AMSM are randomized to either the attention control or intervention condition. Self-completed study assessments are conducted online every three months across the intervention and attention-control follow-up time points, with a total follow-up period of 12 months for participants initially randomized into the intervention group, and 15 months for participants initially randomized into the control group. In months 12 to 15, we will make the intervention accessible to AMSM in the attention-control condition. The primary outcomes are cognitive (e.g., HIV prevention attitudes, norms, self-efficacy, behavioral intentions); behavioral outcomes are secondary (e.g., condom use, HIV testing, PrEP use). The proposed study design thus tests the impact of an e-delivered life skills intervention with an embedded video-chat peer motivational interviewing function on cognitive and behavioral HIV-related outcomes on a large (n=600) sample of AMSM.

The study is funded for approximately 5 years (Project Period: 07/28/2016 to 02/28/2021). Once consented, participants randomized into the intervention group will be active in the study for 12 months. Participants randomized into the control group will be active in the study for 15 months.

METHODS:

1. Study Instruments:

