for 1 peer who could help us contact them), while being sensitive to undue disclosure of AMSM participating in the study. We also have a pre-planned schedule of follow-ups that consists of a variety of follow-up methods. Initially, a respondent who does not respond to an electronic notification that a survey is due will automatically receive additional notifications 36 hours after the initial notification. If the participant has still not completed the assessment 24 hours after the third electronic notification, the retention activities are escalated to a research staff member who will begin escalating contact intensity. Depending on the participants preferences provided upon registration, contacts will be made initially with the preferred mode of re-contact (for example, by SMS text message); if still unresponsive, other available modes (e.g., phone call) will be used. Each contact is logged in an electronic retention system developed by Emory University and used in prior studies to achieve excellent (90%) retention. This system also maintains electronic lists of participants retention status, and automatically creates notification lists for retention staff to ensure that a systematic process is followed and carefully documented for retention.

5. Data Management:

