The research activities involve a two-arm prospective RCT enrolling a sample of 600 AMSM with the aim of maintaining a randomized sample of approximately 500 online-recruited AMSM, assuming 15-20% attrition. After consent and completion of the baseline survey, AMSM are randomized to either the control or experimental condition (Intervention, n=300; Control, n=300). Participants in the control arm will receive access to only the resource locator function of iReach, allowing them to search for local/national resources. Participants in the experimental arm will receive access to all iReach functions, including life skills education, goal setting, a discussion forum related to life skills and goal setting, local/national resource directory, and the ability to link to a peer mentor through the VSee video-chat function. Self-completed study assessments are conducted online every three months across the intervention and attention-control follow-up time points, with a total follow-up period of 12 months. At the end of the trial, we will make the intervention accessible to AMSM in the attention-control condition for a 3 month period, followed by an additional follow-up assessment at month 15. The primary outcomes are cognitive (e.g., HIV prevention attitudes, norms, self-efficacy, behavioral intentions); behavioral outcomes are secondary (e.g., condom use, HIV testing, PrEP use). The proposed study design thus tests the impact of an e-delivered life skills intervention with an embedded video-chat peer motivational interviewing function on cognitive and behavioral HIV-related outcomes on a large (n=600) sample of AMSM.

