Attention Control Condition: Participants randomized to the control condition will receive access only to the Resource Locator embedded within iReach. While the provision of a service locator is a form (albeit weak) of an intervention and may decrease our ability to detect intervention effects, we felt that withholding referrals to services would be unethical given AMSM's vulnerability to HIV and STIs. By providing the existing testing site locator only, we will still be able to test the effect of iReach (i.e., user-tailored content focused on life skills + peer mentor counseling through VSee). Participants initially randomized into the control condition will receive three months of access to the full intervention after they have completed 12 months in the control condition.

Additionally, during months 12 to 15 of participation, we will test whether incentivization of app engagement has any effect on participant utilization of intervention features. Participants initially randomized to the control condition, upon completing 12 months in the attention control condition and receiving three months access to the full intervention, will be informed that they can earn an additional \$40 reward for earning badges totaling 25 points in the iReach app (see image of point system below). See page 14 of this document for a description of iReach badges. Participants will be able to choose which badges they want to pursue, and therefore will be able to choose which intervention actions they complete in order to earn the incentive. Badges are set up to reward incremental use of app features (e.g. badge 1 = read one page, badge 2 = read five pages, etc.). We have developed the point system and chosen the target of 25 points so as to reward moderate use of the app, use which requires meaningful but achievable use. Participants who reach the 25 point target during their three months of full intervention access will earn an additional \$40 Amazon gift card, paid after the completion of the 15 month survey (or timing out of the survey window).

2. Data Collection:

Data will be collected from participants through web surveys at baseline, month 3, month 6, month 9, and month 12 (and month 15 for participants initially randomized into the control condition). For participants who engage in peer mentoring sessions with peer mentors, information about the session will be documented at the time of the session.

3. Genetic Testing:

Not applicable.

4. Use of Deception:

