
5. Protected Health Information

The following PHI identifiers will be collected in this study:

- Name
- Street address, city, county, precinct, zip code, and equivalent geocodes
- All elements of dates (except year) for dates directly related to an individual and all ages over 89
- Telephone numbers
- Electronic mail addresses
- Web addresses (URLs)
- Internet IP addresses
- Biometric identifiers, including finger and voice prints
- Full face photographic images and any comparable images
- Any other unique identifying number, characteristic, or code

6. Compensation and Incentivization:

Compensation for completing the baseline, the 12-month follow-up survey, and the 15-month follow-up survey (for participants initially randomized into the control condition) will be \$30 per assessment, whereas the 3, 6, and 9-month follow-ups will be \$25 each since they are shorter in length.. This compensation is small enough to avoid undue influence, yet sufficiently substantial to compensate for time and effort, and promote retention. Participants will be eligible to receive \$135 - \$165 compensation for completing surveys, depending on which group they are randomly assigned to, if they complete all assessments.

Additionally, participants randomized into the control condition will be eligible to earn a \$40 incentive for intervention use during their three month period of full intervention access from months 12 to 15. Participants earn this incentive for collecting iReach badges totaling 25 points, markers of completing the various actions described in the Experimental Group description above. Given the minimal risks associated with intervention use, this incentive does not constitute an undue influence. Participants randomized into the intervention group will not be eligible for this incentive.

All compensation and incentives will be paid as Amazon gift cards. Payment for the baseline survey will be sent once participants have completed the survey and have responded to the email containing their iReach WebApp login credentials. All subsequent compensation Amazon cards will be sent after the participant completes the associated survey. The incentive will be sent to participants who earn it after the 15 month survey. Participants who earn the incentive but do not complete the 15 month survey will receive the incentive after they time out of the 15 month survey window.

7. Data and Safety Monitoring:

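### Control access to full iReach is timed by the calendar and is not made to wait for the month-12 survey, so the last randomised control assessment could follow crossover

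*Protocol*

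**What the plan says.** Four places in the protocol time the controls' access to the full app:

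- Study Design: "In months 12 to 15, we will make the intervention accessible to AMSM in the attention-control condition".
- Study Procedures, 1. Detailed Description, opening paragraph: "At the end of the trial, we will make the intervention accessible to AMSM in the attention-control condition for a 3 month period", with a further assessment at month 15.
- The same section, Attention Control Condition: controls "will receive three months of access to the full intervention after they have completed 12 months in the control condition". In this period they are also told of a $40 reward for earning 25 badge points.
- Risk/Benefit Assessment, 6. Compensation and Incentivization: the reward is earned "during their three month period of full intervention access from months 12 to 15".

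Methods, 4. Administration of Surveys and 7. Subject Follow-up describe what happens when a survey is not answered on time. Electronic notices are repeated. "If the participant has still not completed the assessment 24 hours after the third electronic notification", then "the retention activities are escalated to a research staff member who will begin escalating contact intensity". A survey window with a time-out is named only for month 15, without a length: the reward is paid to non-responders "after they time out of the 15 month survey window".

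The SAP's assessment table places the primary-outcome domains at baseline and months 6, 12 and 15. Its Efficacy Analyses section models baseline and four follow-ups. Neither document gives a month-12 visit window or says how to treat a control answer given after access has opened.

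**The concern.** Month 12 is the last point at which the randomised arms can be compared. Month 15 is collected in controls only, and by then they have had the intervention. On the SAP's table, months 6 and 12 are therefore the only two post-baseline primary-outcome waves with an unexposed control group. The plan's cross-sectional detectable difference is also stated for the final follow-up.

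If access opens on the date the survey falls due, a control who answers late may do so with life-skills content, peer mentoring and a paid reason to use the app already available. This can happen only in the control arm. If iReach improves knowledge, self-efficacy or intentions, it would raise control scores and shrink the month-12 difference.

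**Working it through.** **1. Is access tied to the survey or to the calendar?** Three of the four statements use elapsed time: months 12 to 15 (twice), and after 12 months in the control condition. The fourth uses a study stage, the end of the trial. None mentions submission of the month-12 survey or the closing of its window.

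**2. Does the timetable leave room for waiting?** Three months of access followed by a month-15 survey gives 12 + 3 = 15, which fits only if access opens at month 12. If access waited x weeks for a late survey, either the access period would shorten by x or the month-15 date would move by x. The protocol provides for neither.

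**3. Does the protocol state survey conditions where it intends them?** Yes. Randomisation follows completion of the baseline survey, login credentials follow its verification, and the $40 is paid on completion or time-out of the month-15 survey. There is no such condition at month 12.

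**4. Are late answers expected?** Yes. If the notices are 36 hours apart throughout (an assumption; only the first interval is given), the third comes at 72 hours and staff contact starts at 72 + 24 = 96 hours, four days after the first notice. How long staff pursue a response is not stated.

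**5. The plan's own figure for this time point.** The plan gives d = 0.22 at 80% power, two-sided 0.05. The formula is (1.960 + 0.842) × √(2/n).

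- n = 250 per arm (protocol): 2.802 × 0.0894 = 0.251.
- n = 300 per arm (SAP): 2.802 × 0.0816 = 0.229.

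The stated 0.22 reproduces with neither; it would need 325 per arm. That is a separate matter. For the illustration I use 0.251, the difference that 250 per arm detects with 80% power.

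**6. Illustration of dilution.** Let f be the share of control month-12 answers given after access opened, and g the share of the full effect those respondents had already gained. Then observed d = 0.251 × (1 − f × g). The documents give no value for f or g, and either may be zero.

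| f | g = 0 | g = 0.25 | g = 0.5 | g = 1 |
|---|---|---|---|---|
| 0% | 0.251 (80%) | 0.251 (80%) | 0.251 (80%) | 0.251 (80%) |
| 10% | 0.251 (80%) | 0.244 (78%) | 0.238 (76%) | 0.226 (71%) |
| 20% | 0.251 (80%) | 0.238 (76%) | 0.226 (71%) | 0.201 (61%) |
| 30% | 0.251 (80%) | 0.232 (74%) | 0.213 (66%) | 0.175 (50%) |

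Each cell shows observed d, with power at 250 per arm in brackets. The g = 1 column is an extreme bound, since it credits a late respondent with a full year's effect. If gains built up evenly over the year (an assumption), one week of use would give g = 1/52 = 0.019. With f = 30% the loss is 0.30 × 0.019 = 0.6% of the effect: observed d = 0.249 and power about 79.5%.

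**The case against.** The strongest reply is that the documents leave the software trigger unstated. Months 12 to 15 may simply name a study phase. The Detailed Description first sets out 12 months of follow-up and then gives access at the end of the trial, which can be read as access after the month-12 assessment. This stands: no section says that access opens whether or not the survey is in.

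Second, access is not use. Mentoring has to be requested and scheduled, and a young man who is ignoring survey notices may well be ignoring the app too. This also stands, although the app menu lists surveys alongside the life-skills content and controls are offered money to use it.

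Third, a window is named only for month 15, so how long month-12 surveys stayed open is unknown. Fourth, any bias is conservative: it cannot create a false finding of efficacy.

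A reader might infer that late controls did answer after exposure, or that a substantial part of the month-12 effect is lost. The documents support neither. They contain no response times and no app-use data for this period. The stated 0.22 is a minimum detectable difference, not an expected effect.

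What survives is that a calendar rule, followed literally, allows the problem, and nothing in either document prevents or detects it.

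**Conclusion.** The point holds as a gap in the design rules, not as demonstrated contamination. Access is described by the calendar, the month-12 survey is due at the same moment, late answers are planned for, and the SAP has no rule for them. If iReach works and some controls use it before answering, the month-12 contrast is biased towards no effect. The bias could be zero and may well be small. Its size depends on two quantities, the share of late control answers and the benefit gained by then, and the documents give neither. The table above illustrates sensitivity and is not an estimate. The change is worth making because it is cheap and protects the last randomised comparison.

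**What to change.** **Protocol.** Reconcile the four access statements (Study Design; Detailed Description; Attention Control Condition; Compensation and Incentivization) into one rule. Unlock the full app and send the badge offer only when the participant's month-12 survey has been submitted or its window has closed, whichever is first. State the length of that window. Run the three months of access and the month-15 due date from the unlock. This follows the completed-or-timed-out form the protocol already uses for paying the $40.

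**SAP, for controls already crossed over.** Use survey submission times (assumed to be retained by the survey platform) and the app-use paradata listed under Study Instruments to report how many month-12 control surveys followed first full-app use. Keep all randomised participants as the primary analysis. Add a sensitivity analysis that sets aside month-12 surveys submitted later than a fixed number of days after the due date, with the same cut-off in both arms. Do not exclude late controls alone: that would select on post-randomisation behaviour in one arm only. The symmetric version still conditions on response time, so it should remain a sensitivity analysis.

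**Cost.** One access rule in the WebApp, a sentence or two in the protocol and a short paragraph in the SAP. Late responders receive access slightly later, with the full three months preserved.

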We propose to enroll 600 AMSM and maintain a sample of 500 AMSM. We will use census information of population structure by race/ethnicity for each region to inform our recruitment goals. We will calculate the number of men in the eligible age group and by race/ethnicity in each region, and use data from the Youth Behavioral Risk Factor Surveillance System (YRBS) to estimate the proportion of AMSM in each age group who could meet eligibility criteria (based on same sex behavior, identity, or attraction), and apply that age-specific proportion to the estimated total AMSM population by race in each region. This will result in an estimated number of eligible AMSM per region and racial/ethnic group. Based on these calculations, to recruit a sample that is diverse in terms of race/ethnicity, we will need to oversample some racial/ethnic subgroups substantially. We will enroll a total of 150 AMSM from each of the 4 regions listed above. As noted, these regions were selected to represent variations in socioeconomic status, HIV prevalence, and rurality. Based on our estimates, we propose to sample such that at least 50% of our sample is a racial or ethnic minority, and at least 35% of participants being from rural areas across the regions. We recognize the challenge of recruiting early adolescents, especially because same sex attraction and same sex sexual experience become more common with age. Therefore, we realistically expect to include a greater number of participants in older age groups. These procedures will provide power for an analysis of efficacy stratified by age and race/ethnicity. Our expected sample size for analyses across both conditions is N=500 (Intervention, n=250; Control, n=250), assuming a 15-20% loss to follow-up. We estimated the minimum detectable effect sizes at 80% power, for comparisons of the two groups for the continuous primary cognitive (e.g., behavioral intentions, attitudes, norms, self-efficacy) outcomes, as well as the difference in the proportion of AMSM who report increased behavioral in the outcomes (e.g., condom use, HIV testing) to engage in HIV prevention services and behaviors in our treatment arm (iReach) vs. our attention-control arm. For mean differences, our sample size calculations are based on a two-sample t-test assuming equal variance using a two-sided significance of 0.05. At 80% power, we are able to detect a between-arm difference of $d=0.22$ at the final follow-up. For repeated measure analyses, assuming a within-person correlation of 0.25, we would be able to detect a difference of 0.08. A less favorable within-person correlation of 0.75 allows us to detect an effect size of 0.11. For proportions, our sample size calculations are based on a two-sample test of proportions using a two-sided significance of 0.05. To have 80% power to compare active treatment to the control group, we require at least 500 participants to find a 12.5% difference between treatment and control in cross-sectional analyses. Assuming within person correlation of 0.25, we can detect an 8.8% difference. A less favorable within-person correlation of 0.75 allows us to detect an 11.3% difference

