
3. Method for Assigning Subjects to Groups:

Eligible participants will complete a baseline survey and subsequently assigned in a 1:1 ratio using a stratified randomization by race and region into the Intervention or Attention-Control condition. Participants recruited nationally will be assigned to a fifth “region” and randomized in a 1:1 ratio to the Intervention or Attention-Control condition.

4. Administration of Surveys and/or Process:

Surveys: We will collect survey data via online self-completed surveys administered at baseline, and 3, 6, 9, and 12 months, with an additional 15 months survey for control participants. Each survey will last approximately 30 minutes. Participants will enter their own responses to questions directly into the survey on their personal computer, smartphone or tablet. Participants will access the surveys via their profile on their password protected study website account. A total of 6 surveys will be conducted, for a total follow-up period of 15 months. The small time frames between assessments will help us to respond quickly to retention concerns. In addition, we have planned our incentive schedule to reflect the time that participants must spend completing the surveys. Incentives for completing the baseline, the 12-month follow-up survey, and the 15-month follow-up survey (for participants initially randomized into the control condition) will be \$30 per assessment, whereas the 3, 6, and 9-month follow-ups will be \$25 each since they are shorter in length. These incentives are small enough to avoid coercion, yet sufficiently substantial to promote retention. In order for interventions to be evaluated as potential best evidence-based interventions through CDCs Prevention Synthesis Research activity, data must be available for at least a single follow-up time point for at least 70% of participants. As indicated below, a detailed retention plan for the study will draw on previously successful retention protocols to achieve at least an 80% retention rate for the first follow-up visit. Our experience has shown that successful retention has several key elements. First, it is critical to obtain accurate follow-up contact information. We will use best practices to retain participants (e.g., comprehensive locator information that includes participants' cell phone number, e-mail, Facebook and/ or other social media usernames, and contact information

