Eligible individuals must (1) have been assigned a male sex at birth and identify as male at the time of enrollment into the study (cis-gender male), (2) be between the ages of 13 and 18 years (inclusive), (3) speak and read English, (4) report same-sex attractions and/or behaviors, (5) have access to the Internet, (6) live in one of the zip codes at least partially contained in the 109 counties included in the four regions selected for this trial, and (7) self-report as HIV-negative at time of enrollment.

Randomization and Blinding

Participants are randomized on a 1:1 basis using a stratified randomization by race and region. AMSM will be randomized to one of two arms, with 300 randomized to each arm (complete data on 250 AMSM per arm, allowing for attrition of 50 AMSM per arm).

Study Assessments

The proposed domains mirror the theoretical framework informing our intervention. We include a summary of the primary and secondary outcomes, key intervention mechanisms of change, and potential covariates. Assessments will not take more than 25 minutes to complete. We have taken several steps to ensure that the assessments are brief and developmentally appropriate. First, AMSM will not answer all listed constructs at every assessment. Identity-related constructs, for example, will be measured at 6-month intervals, whereas other constructs (e.g., comfort discussing sexuality) will be assessed at each follow-up. Second, consistent with best practices that we have used in prior HIV studies with pediatric and adolescent populations^{142,256}, we will use gate-keeping questions to decide whether participants should receive other probes within a domain. For example, a participant who has yet to become sexually active would receive cognitive assessments focused on HIV risk and awareness (e.g., attitudes, norms), but would not receive questions regarding behavioral intentions to engage in HIV prevention in next 3 months (e.g., HIV testing, PrEP) or questions regarding sexual risk behaviors (e.g., sexual behavior, HIV testing, PrEP use). Similarly, at each assessment, AMSM with no lifetime substance use will not be asked about additional substance use questions. Among sexually active participants, gatekeeping also provides opportunities to regulate how detailed the assessments will be.

Domain	Assessment time					
	Baseline	Month 3	Month 6	Month 9	Month 12	Month 15
Primary outcomes						
HIV knowledge	X		X		X	X
Condom use/communication efficacy	X		X		X	X

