To allow for 15-20% loss to follow-up (our previous trials have each achieved retention rates of >90%), we estimate a sample of 600 AMSM to be enrolled across the four regions. Participants may continue the study even if they miss surveys intermittently over the data collection period. We will compare those who completed different follow-up interviews with those who did not on key predictors from the baseline assessment to check for possible sampling bias due to missing data. Missing data will be minimized by the web-based entry for all measures. We will handle missing data by applying likelihood-based methods that include partial information in cases that drop out prematurely and develop nonresponse adjustment and post-stratification weights to account for survey non-participation. The use of Expectation-Maximization (EM) algorithm and multiple imputation approach

in longitudinal analyses will help overcome missing data concerns when appropriate. When the missing at random assumption appears suspect, we will not replace missing data to avoid bias.

Summary of Study Data

All continuous variables will be summarized using the following descriptive statistics: n (non-missing sample size), mean, standard deviation, median, maximum, and minimum. The frequency and percentages (based on the non-missing sample size) of observed levels will be reported for all categorical measures. In general, all data will be listed, sorted by site, treatment, and subject, and when appropriate by visit number within subject. All summary tables will be structured with a column for each treatment in the order (Control, Experimental) and will be annotated with the total population size relevant to that table/treatment, including any missing observations.

Efficacy Analyses

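### Enrolling 600 leaves the required 500 only if loss stays at or below 16.7%; the upper end of the plan's own 15-20% range leaves 480

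*Protocol*

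**What the plan says.** The Protocol, under Target Population and Accrual, sets the two counts: "We propose to enroll 600 AMSM and maintain a sample of 500 AMSM". The same section continues: "Our expected sample size for analyses across both conditions is N=500 (Intervention, n=250; Control, n=250), assuming a 15-20% loss to follow-up". For proportions it says "we require at least 500 participants to find a 12.5% difference between treatment and control in cross-sectional analyses", at 80% power and a two-sided 0.05 level. The Study Design section and the Detailed Description under Study Procedures repeat 600 enrolled, approximately 500 maintained, and 15-20% attrition.

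The SAP gives the allowance as a count under Randomization and Blinding: "complete data on 250 AMSM per arm, allowing for attrition of 50 AMSM per arm". Its Missing Data section returns to the range: "To allow for 15-20% loss to follow-up (our previous trials have each achieved retention rates of >90%), we estimate a sample of 600 AMSM". Its Sample Size section repeats the requirement of 500, but gives 600 (300 per arm) as the expected sample for analyses while assuming the same 15-20% loss.

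The Protocol's section on Administration of Surveys and/or Process describes a retention plan intended "to achieve at least an 80% retention rate for the first follow-up visit". The first follow-up is month 3.

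**The concern.** Three planning figures should fit together: the number enrolled, the loss assumed, and the number needed for the stated power. They fit at the lower end of the loss range but not at the upper end. A loss between 16.7% and 20% is within what the plan expects, yet it takes the sample below what the plan says it requires. The documents also give more than one figure for the analysed sample: 500 in the Protocol, 250 per arm in the SAP's randomisation section, and 600 after loss in the SAP's Sample Size section. A reader cannot tell which figure the detectable effects rest on if loss reaches 20%. In addition, the month-12 goal that matches the power statement appears only as a count and never as a completion rate for that survey.

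**Working it through.** **Inputs from the documents.** Enrolled: 600, allocated 1:1. Loss: 15-20%. Required: at least 500 (250 per arm) for 12.5 points, 80% power, two-sided 0.05. SAP allowance: 50 of 300 per arm. Retention benchmark: at least 80% at month 3.

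**Assumption.** No control proportion is given. I use 0.4375 and 0.50, which come close to the plan's figure, and show 0.30 and 0.20 as a range.

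**Step 1: reproduce the stated 500.** With pooled variance under the null and no continuity correction,

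n per arm = [1.960 × √(2p̄(1−p̄)) + 0.842 × √(p₁(1−p₁) + p₂(1−p₂))]² / (p₂−p₁)².

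- 0.4375 vs 0.5625: (1.960 × 0.7071 + 0.842 × 0.7016)² / 0.015625 gives 250 per arm, 500 in total.
- 0.50 vs 0.625: 247 per arm, 494 in total.

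So 500 is a sound figure for the number analysed.

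**Step 2: what 600 leaves.** Retained = 600 × (1 − loss).

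| Loss | Retained |
|---|---|
| 15% | 510 |
| 16.7% (50 of 300 per arm) | 500 |
| 20% | 480 |

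In reverse, 500 / 600 = 83.3% must be retained, and 500 / (1 − 0.20) = 625 would have to be enrolled to keep 500 after 20% loss. The figure 600 equals 500 × 1.20, so multiplying where one should divide would produce it. The documents do not say how it was derived.

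**Step 3: cost of 480 for proportions.** Power = Φ{[(p₂−p₁)√n − 1.960 × √(2p̄(1−p̄))] / √(p₁(1−p₁) + p₂(1−p₂))}, with n per arm.

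| Control vs intervention | Power at 250 per arm | Power at 240 per arm |
|---|---|---|
| 0.4375 vs 0.5625 | 80.0% | 78.4% |
| 0.50 vs 0.625 | 80.6% | 79.0% |
| 0.30 vs 0.425 | 83.0% | 81.5% |
| 0.20 vs 0.325 | 89.0% | 87.8% |

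Solving for the difference that gives 80% power at 240 per arm yields 12.7 points (control 0.50) to 12.8 points (control 0.4375). At 250 per arm the values are 12.4 and 12.5.

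**Step 4: cost for means.** Detectable d = (1.960 + 0.842) × √(2/n). At 250 per arm this is 0.251 and at 240 per arm 0.256, a change of 0.005.

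**The case against.** The best defence is that the plan describes a range around approximately 500, and 480 to 510 is such a range. The retained goal is already written as a count: 500 in the Protocol, and 250 per arm in the SAP, which is exactly 83.3%. Prior retention of 90% or more is cited. The requirement of 500 is attached to cross-sectional tests of proportions, and the condom-use and HIV-testing outcomes named there are behavioural, which the Protocol's Study Design section calls secondary. The main analysis is intention-to-treat with likelihood-based mixed models that use partial data. Much of this stands, and it is why the point is minor. It does not remove the inconsistency. The plan's assumption is 15-20% rather than 10%, the requirement is worded as a minimum, and partial data from other waves do not restore the number available for a cross-sectional comparison.

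Three stronger readings are tempting, and the documents do not support them.

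- A reader might infer that 80% at month 3 already fixes the trial at 480 or fewer by month 12, with further loss to come. For example, 5% lost at each of three later waves would give 480 × 0.95³ ≈ 412. The documents give no per-wave loss rates, and the SAP's Missing Data section lets participants miss surveys and continue, so month-3 response does not cap month-12 response. The SAP's assessment table also schedules no primary outcome at month 3.
- A reader might infer that the 80% figure is the basis for power, set at the wrong wave. In the Protocol it directly follows a 70% evidence-review criterion for a single follow-up and reads as a margin over that criterion. The reminder and escalation steps apply whenever a survey is due.
- A reader might set 0.256 beside the plan's stated d of 0.22 and blame attrition. At 500 the two-sided detectable value is already 0.251, so nearly all of that gap is a separate matter.

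**Conclusion.** The inconsistency is real and minor. The upper end of the stated loss range leaves 480 of 600, which is 20 short of the stated minimum. The SAP's own allowance corresponds to 16.7%. If loss reaches 20%, power for a 12.5-point difference falls by about 1.6 percentage points, to 78.4-79.0%, and the detectable difference rises to about 12.7-12.8 points. These sizes assume a control proportion of 0.44 to 0.50. At 0.30 or 0.20, power at 480 stays above 80%. At 15% loss there is no shortfall.

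Treating 500 as the sample needed at month 12 joins two statements, because the Protocol attaches the final follow-up to the difference in means and the minimum of 500 to cross-sectional proportions. That is a fair reading, since 500 is described as the sample left after loss, but no single sentence says it.

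**What to change.** 1. In the Protocol (Target Population and Accrual; Study Design; Detailed Description) and the SAP (Sample Size; Missing Data), choose one of two wordings. Either replace 15-20% with loss of up to 16.7%, matching 50 of 300 per arm, or keep 20% as the upper limit and restate the analysed sample as 480 (240 per arm). The second choice needs the detectable effects restated: about 12.7-12.8 points for proportions with the assumed control proportion named, and 0.256 for means on a two-sided test. The repeated-measures figures would be recalculated on the same sample.
2. In the SAP's Sample Size section, replace 600 (300 per arm) as the expected sample for analyses after loss with the figure chosen in item 1, and keep 600 as the number randomised.
3. In the Protocol's section on Administration of Surveys and/or Process, keep the 80% first-follow-up benchmark and add beside it the month-12 goal that matches the power statement: at least 250 of 300 in each arm (83.3%) completing the month-12 survey.

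The cost is wording in two documents and, if 20% is kept, a slightly less favourable stated figure. No extra enrolment is needed.
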